### 7.5.4 Transfusion Independence

Transfusion independence (TI) will be analyzed separately and simultaneously for platelet and RBC transfusions. Transfusion dependence (TD) and transfusion independence are defined as follows:

- Transfusion dependence at baseline: documentation of 2 units or more of transfusion within 56 days of the first dose of study treatment.
- Post-treatment transfusion independence: no transfusion for 56 consecutive days or more after the first dose of study treatment while maintaining hemoglobin  $\geq 8$  g/dL (RBC TI) or maintaining platelets  $\geq 20 \times 10^9/L$  (platelet TI).

Post-treatment transfusion independence rate will be calculated separately and simultaneously for RBC transfusion independence and platelet transfusion independence as the number of subjects who are transfusion independent post treatment (n) among those who were transfusion dependent at baseline (N). The 95% Clopper-Pearson CI for transfusion independence rates will be provided. The same analyses will be performed for 84-day and 112-day transfusion independence, defined as no transfusion for 84 consecutive and 112 consecutive days, respectively, while maintaining hemoglobin  $\geq 8$  g/dL (RBC TI) or maintaining platelets  $\geq 20 \times 10^9/L$  (platelet TI).

### 7.5.5 Overall Survival

Overall survival (OS) is defined as the number of days from the date the subject was randomized to the date of death (regardless of cause). In the absence of documented death at the time of analysis, the OS time will be censored on the last date the subject is known alive.

The Kaplan-Meier plot will be provided based on the Efficacy Analysis Set. The median (and quartiles) duration of OS and the associated 95% CI will be estimated using the Kaplan-Meier method and the log-log transformation for the survival function. In addition, subject follow-up time in days will also be summarized.

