# 9.5.2 Screening / Baseline Procedures

After the investigator or sub-investigator confirms that a subject is eligible and willing to participate in the study, study center personnel will forward the appropriate documentation to the attention of the sponsor according to the study procedures manual.

Within 14 days before treatment administration (or as specified below or in Table 9), perform the following study procedures and tests:

- Legally effective informed consent. The ICF must be signed and dated by the subject before any study-specific samples are collected or study-specific procedures are initiated.
- Investigator's confirmation of eligibility. Perform all necessary procedures and evaluations to document that the subject meets each eligibility criterion.
- Assess IPSS and any prior cancer treatments.
- Complete medical history, including demographics. Record disease history, including the date
  of initial diagnosis. Document concurrent medical signs and symptoms to establish baseline
  conditions.
- Randomization (confirm with medical monitor): see Section 6.1.
- Complete physical exam (PE) including height and weight, and examination of body systems.
- Obtain height and weight; perform BSA calculation. Use Screening BSA for calculation of IV decitabine dose (for IV decitabine cycle).
- Vital signs include resting systolic/diastolic blood pressure, resting respiration rate, resting heart rate, and body temperature.
- ECOG performance status (see Appendix 1).
- 12-lead ECG: single tracing only unless clinically significant abnormality for which triplicate ECG is preferred for confirmation, eg, QTc >500 msec; rhythm, atrial rate, ventricular rate, PR interval, QRS duration, and QT/QTc, and overall interpretation. Either the Bazett's or Fridericia's formula may be used to calculate the QTc interval but must be used consistently throughout the study.
- ECHO or MUGA: may be performed up to 28 days before study treatment.
- Record concomitant medications.
- Transfusion requirements: record transfusions received since previous assessment time point: up to 56 days prior if data are available.
- Collect blood samples for hematology and serum chemistry, and urine sample for urinalysis.
- Serum or urine pregnancy test: for women of child-bearing potential only. Results must be negative for the subject to be eligible for enrollment into the study.

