# 11.2.3 Efficacy Analysis Set

The Efficacy Analysis Set will include data from all subjects who received at least one full dose (day) of study treatment. All data will be included, and no subjects excluded because of protocol violations. Subjects will be included in the treatment group according to their randomly assigned treatment.

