#### 11.7.3 Leukemia-Free Survival

The number of days from randomization to the date when bone marrow or peripheral blood blasts reach  $\geq$ 20%, or death from any cause, will be measured for subjects in the Efficacy Analysis Set. Subjects who do not have events in leukemia-free survival will be censored on the last date of bone marrow or peripheral blood blasts assessment, whichever is later. Subjects who have bone marrow or peripheral blood blasts  $\geq$ 20% at baseline will be censored at the date of randomization. Leukemia-free survival will be presented using a Kaplan-Meier estimate. The 95% CI for the median of leukemia-free survival will be provided using the Kaplan-Meier procedure.

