### **5.2 Randomized Subject Analysis Set**

The Randomized Subject Analysis Set will include data from all subjects who were randomized into the study. Subjects will be included in the treatment group according to their randomly assigned treatment.

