### **5.3 Efficacy Analysis Set**

The Efficacy Analysis Set will include data from all subjects who received any amount of study treatment. All data will be included, and no subjects excluded because of protocol deviations. Subjects will be included in the treatment sequence according to their randomly assigned treatment sequence.

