### **7.5.6 Survival Rate at 6 Months, One Year and Two Years**

One-year survival rate is defined as the survival rate at the end of the first year from randomization.

One-year survival rate and the associated 95% CI will be estimated by Kaplan-Meier procedure with the log-log transformation. The survival rates at 6 months and 2 years will be similarly summarized.

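### Survival endpoints are counted from randomization but analysed only in treated subjects, so deaths before the first dose are left out of the curves and survival could be slightly overstated

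*SAP*

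**What the plan says.** **SAP (AML).** Section 7.5.5 counts overall survival (OS) from randomization to death, and then says: "The Kaplan-Meier plot will be provided based on the Efficacy Analysis Set". Sections 7.5.7 and 7.5.8 use the same starting point and the same set for event-free survival (EFS) and progression-free survival (PFS). Section 7.5.6 fixes the origin of the landmark rates: "One-year survival rate is defined as the survival rate at the end of the first year from randomization", with 6 months and two years handled alike.

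Membership of the set depends on a later event. Section 5.3 states: "The Efficacy Analysis Set will include data from all subjects who received any amount of study treatment". Section 5.2 also defines a wider set: "The Randomized Subject Analysis Set will include data from all subjects who were randomized into the study". Sections 7.1 and 7.2 use that wider set only for disposition and for demographic and baseline summaries. Time to response (7.5.2), in contrast, starts at first treatment.

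**Protocol (MDS/CMML).** Section 11.7.3 counts leukemia-free survival (LFS) from randomization, and it "will be measured for subjects in the Efficacy Analysis Set". OS in 11.7.4 also starts at randomization and takes the same set by the default rule in 11.7. The protocol's set is narrower than the SAP's: "all subjects who received at least one full dose (day) of study treatment" (11.2.3).

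**Timing.** Protocol 9.5.2 lists randomization among the procedures to be done "Within 14 days before treatment administration". Section 6.1 asks that treatment begin as soon as possible after randomization. Neither gives a separate limit for the interval between the two.

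**The concern.** The clock and the population do not match. To be in the analysis set a subject must be alive at the first dose, yet follow-up is counted from an earlier date. Nobody in the set can die in the interval between the two, and a randomized subject who does die then is not in the set. The curve therefore estimates survival given that the subject lived to be dosed, while it is labelled as survival from randomization.

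At stake are the reported median OS and the landmark survival rates, and to a less definite degree EFS, PFS and LFS. SAP 6.0 plans the analysis for a submission, and SAP 1.1 describes high mortality in older AML patients, where death before dosing is plausible. No analysis with matched clock and population is planned, so the curves themselves would not reveal the effect.

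**Working it through.** The documents state no event number, precision or power for the survival endpoints, so there is no plan figure to reproduce. The pharmacokinetic sample size does not depend on this choice.

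**Inputs**
- About 85 AML subjects randomized (SAP 4.0).
- Interval *d* from randomization to first dose: not stated. I use 7 and 14 days. Fourteen is the limit of the screening window in the supplied US protocol; the European and Canadian AML protocols behind the SAP are not supplied.
- Median survival of 6 to 10 months: my assumption.
- Exponential survival, with deaths before dosing at the same hazard: my assumption.

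**Formula.** With λ = ln 2 / median, survival from randomization in all randomized subjects is S(t) = exp(−λt). Among those alive at first dose it is S(t)/S(d) = exp(−λ(t − d)) = S(t − d). The overstatement is S(t − d) − S(t). Expected deaths before dosing are 85 × (1 − S(d)).

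**Results at t = 6 months (182.6 days)**

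| Median | S(t) | Overstatement, d = 7 | Overstatement, d = 14 | Expected pre-dose deaths of 85 (d = 7; d = 14) |
|---|---|---|---|---|
| 6 months | 0.500 | 1.35 points | 2.73 points | 2.2; 4.4 |
| 8 months | 0.595 | 1.20 points | 2.42 points | 1.7; 3.3 |
| 10 months | 0.660 | 1.06 points | 2.14 points | 1.3; 2.7 |

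For the 8-month median and 14 days: S(d) = 1 − 3.32/85 = 0.961, and 0.595/0.961 = 0.619, a difference of 2.4 points.

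**One bias, not two.** The identity S(t)/S(d) = S(t − d) shows that dropping the pre-dose deaths and adding guaranteed survival time are the same effect described twice. Per dropped death, with all-randomized survival of 0.595, the effect is 0.595 × 85/84 − 0.595 = 0.7 points. Multiplying by the 3.3 expected deaths gives about 2.3, which is the 2.4 above up to rounding and curvature. The two figures must not be added.

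**A cross-check at one year.** SAP 1.1 cites 12-month survival of 25% to 30% for AML patients aged 65 to 74. Used as an assumption in the same formula, this gives about 0.7 points for 7 days and 1.4 points for 14 days.

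**Lower-risk MDS.** Protocol 1.1 cites median survival of 3.5 to 5.7 years. With those medians, a 7-day interval changes 6-month survival by only 0.2 to 0.3 points.

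**Zero case.** If all 85 are dosed, the two sets are identical and the overstatement is 0, however long the interval.

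**The case against.** The strongest reply is that little depends on this. Efficacy is descriptive, with no formal comparison between sequences (SAP 7.5); the protocol pools it as one group (11.7); and the design gives each subject both drugs in the first two cycles. No randomized survival contrast is damaged. Dosing is meant to follow randomization promptly, and randomization comes after the medical monitor confirms eligibility (protocol 6.0), so 14 days is a ceiling and not a typical interval. The supplied protocol also requires a life expectancy of at least 3 months and excludes rapidly progressive disease, which should lower early deaths below a constant hazard. All of this stands, and it keeps the point small.

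Three stronger readings are tempting, and the documents do not support them:

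- **That the excluded subjects disappear from the report.** Disposition covers all randomized subjects and includes death and consent withdrawal as reasons (SAP 7.1). SAP 7.0 also plans listings of all deaths and of subjects excluded from the efficacy analysis. They are missing only from the curves and rates.
- **That the bias always favours the trial.** This is true of pre-dose deaths. A pre-dose withdrawal without further follow-up would be censored near day 0 and would hardly move the curve. One who lived long on other treatment would raise survival among all randomized subjects.
- **That EFS, PFS and LFS are biased by the same amount.** Only death is ruled out before dosing. Progression, or blasts reaching the LFS threshold, can occur in that interval in a subject who is later dosed. LFS is not an endpoint of the supplied SAP, and the separate MDS/CMML SAP is not available to check.

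**Conclusion.** The mismatch is in the text of both documents, and for deaths before dosing it can only raise the survival estimate. Whether it has any effect depends on how many randomized subjects are never treated and what happens to them, which the documents do not say. The right statement is that survival could be overstated, not that it is.

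Under the stated assumptions the size is about 1.1 to 1.4 points on 6-month survival for a 7-day interval and 2.1 to 2.7 points at the 14-day ceiling. These figures rest on an exponential curve, a 6-to-10-month median, equal hazard before and after randomization and dosing, and a window borrowed from a protocol other than the AML one. They already include the dropped deaths. No size is given for EFS, PFS or LFS.

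This is a minor, inexpensive correction to secondary descriptive endpoints. The primary equivalence analysis is untouched.

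**What to change.** In SAP 7.5.5 to 7.5.8, replace the Efficacy Analysis Set with the Randomized Subject Analysis Set of SAP 5.2 and keep randomization as the origin. If a treated-only version is also wanted, start its clock at the first dose, as SAP 7.5.2 already does for time to response. Report the number randomized but not treated, their vital status, and the distribution of the interval from randomization to first dose. Apply the same rule to protocol 11.7.3 and 11.7.4, and check the separate MDS/CMML SAP for it.

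The cost is mostly wording and a population flag. The figures may become slightly less favourable. Vital status may have to be obtained for a few never-treated subjects, because protocol 9.5.6 schedules survival contact for those who have stopped treatment. Without that follow-up they would be censored early and the change would do little. Changing the protocol text would need an amendment. The first-dose clock for a treated-only version needs no extra follow-up.

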### **7.5.6 Survival Rate at 6 Months, One Year and Two Years**

One-year survival rate is defined as the survival rate at the end of the first year from randomization.

One-year survival rate and the associated 95% CI will be estimated by Kaplan-Meier procedure with the log-log transformation. The survival rates at 6 months and 2 years will be similarly summarized.

### **7.5.7 Event-Free Survival**

Event-free survival (EFS) was not described in the study protocol and was added in this SAP. EFS is defined as the number of days from the date of randomization to the date of treatment failure (disease progression/relapse, discontinue treatment due to disease progression or treatment-related adverse event, or alternative anti-leukemia therapy except for HCT) or death from any cause, whichever occurs first. In the absence of any of these events at the time of analysis, EFS time will be censored on the last date the subject is known alive. Subjects who do not have post-baseline information will be censored at the date of randomization. The Kaplan-Meier plot will be provided based on the Efficacy Analysis Set. Estimated median survival time (days) and 95% CIs will also be provided if available.

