#### 9.5.6 Survival/Conversion to AML

Follow all subjects for survival/conversion to AML who have stopped study treatment. Contact subject every 3 months until death or withdrawal of consent or the close of the trial. This assessment may be conducted by telephone.

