### 7.5.3 Duration of Response

A combined duration of CR and CRh (in number of days) will be calculated from the first time a CR or CRh is observed to the date of the earliest of the following 3 events: (1) relapse (defined as the earliest time point whereby BM assessment or PB assessment by the investigator indicate relapse/disease progression due to confirmed reappearance of leukemic blasts in PB or  $\geq 5\%$  leukemic blasts in BM, or clinical progression determined by the investigator), (2) start of alternative therapy (except hematopoietic cell transplantation [HCT]) or (3) death. In the absence of any event, the combined duration of CR and CRh will be censored at the last available time point (BM assessment, PB assessment, or safety/long-term follow-up visit) at which an event was not observed. Duration of combined CR and CRh will be analyzed using the Kaplan-Meier method for subjects who achieved a CR or CRh during the study; the median and quartiles of the duration, as well as their respective 95% CIs will be provided. Duration of CR or CRp and duration of CR will be calculated and analyzed similarly.

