### **7.5.8 Progression-free Survival**

Progression-free (PFS) survival was not described in the study protocol and was added in this SAP. PFS is defined as the number of days from the date of randomization to the date of disease progression (including relapse) or death from any cause, whichever occurs first. In the absence of disease progression or death at the time of analysis, PFS time will be censored on the last date the subject is known alive. The Kaplan-Meier plot will be provided based on the Efficacy Analysis Set. Estimated median survival time (days) and 95% CIs will also be provided if available.

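### Event-free survival counts progression and relapse but is censored at the last date known alive, which biases the descriptive EFS estimate upward by an amount the documents cannot fix

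*SAP*

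**What the plan says.** SAP 7.5.7 measures EFS from randomization to treatment failure or death. Treatment failure means "disease progression/relapse, discontinue treatment due to disease progression or treatment-related adverse event, or alternative anti-leukemia therapy except for HCT". If none of these has occurred, "EFS time will be censored on the last date the subject is known alive", which is the rule that SAP 7.5.5 uses for overall survival. There is one exception: "Subjects who do not have post-baseline information will be censored at the date of randomization". What counts as post-baseline information is not defined. PFS in SAP 7.5.8 is treated alike: "PFS time will be censored on the last date the subject is known alive". Neither section sets a rule for missed assessments or plans a sensitivity analysis.

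Two other endpoints tie censoring to disease status. In SAP 7.5.3, duration of CR/CRh without an event "will be censored at the last available time point (BM assessment, PB assessment, or safety/long-term follow-up visit) at which an event was not observed". In protocol 11.7.3, subjects without a leukemia-free survival (LFS) event "will be censored on the last date of bone marrow or peripheral blood blasts assessment, whichever is later".

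For subjects who have stopped study treatment, protocol 9.5.6 provides survival and AML-conversion follow-up: "Contact subject every 3 months until death or withdrawal of consent or the close of the trial. This assessment may be conducted by telephone". Protocol Table 9 schedules marrow at screening and from Cycle 3 onward, with none at treatment discontinuation or the 30-day visit.

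SAP 7.5 makes efficacy descriptive, with no formal comparison between sequences.

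**The concern.** Knowing that a subject is alive shows that death has not happened. It does not show that progression or relapse has not happened. Some ways of leaving treatment are not EFS events: the subject's own decision, an adverse event unrelated to treatment, and transplant, which 7.5.7 expressly leaves out. If disease assessment ends there and survival contact continues, each contact lengthens event-free time. An unseen relapse is then either missed or dated late, at death.

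EFS has no control arm against which such a bias could cancel. The curve and median are themselves the reported result, in the analysis that SAP 6.0 describes as being for submission.

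**Working it through.** **No figure to reproduce.** The documents give no EFS median, event rate or event count. The check is therefore of direction, followed by an illustration of size.

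**Direction.** Let E be the true EFS time, D the time of death and A the data cut-off. For a subject whose assessments stop before E, and for whom only death is detected later, the SAP rule records min(D, A) in place of min(E, A). Since D is never earlier than E, the recorded time is never too short. If the cut-off is unrelated to prognosis, the Kaplan-Meier curve estimates the distribution of a time at least as long as EFS. The bias is upward, and zero if nobody stops assessment early.

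**Illustration 1 (every input assumed).** E is exponential with median 6 months, so its hazard is ln 2 / 6 = 0.1155 per month. Survival after the event has median 5 months. Cut-off is uniform over 6 to 29 months. Assessments stop independently at rate r. Ignoring the cut-off, the proportion stopping before an event is r / (r + 0.1155). For r = 0.01 this is 0.01 / 0.1255 = 8%, and for r = 0.03 it is 0.03 / 0.1455 = 21%. With the cut-off the proportions are 7% and 18%.

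Median EFS in months (true value 6.0):

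| r per month | Stop early | SAP rule, only death detected later | SAP rule, half of unseen failures surface as new therapy | SAP rule, 80% surface | LFS-style rule | Last assessment, later deaths censored |
|---|---|---|---|---|---|---|
| 1% | 7% | 6.2 | 6.1 | 6.1 | 6.1 | 6.0 |
| 3% | 18% | 6.5–6.6 | 6.4 | 6.2–6.3 | 6.2 | 6.0 |
| 6% | 31% | 7.2 | 6.7 | 6.5 | 6.4 | 6.0 |
| 10% | 44% | 8.1 | 7.2 | 6.8 | 6.7 | 6.0 |

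The new-therapy columns assume a median delay of 1 month from failure to new therapy. The LFS-style column censors survivors at the last assessment but still counts later deaths at the death date.

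**Illustration 2 (also assumed).** Progression or other failure has median 6 or 9 months, death without progression 30 months, post-progression survival 5 months, and cut-off is uniform over 6 to 24 months. The true EFS medians are 1 / (1/6 + 1/30) = 5.0 and 1 / (1/9 + 1/30) = 6.9 months. The SAP rule gives 5.2 months when 9% stop assessment early and 6.1 when 38% do, against 5.0. In the second case it gives 7.1 at 8% and 8.1 at 35%, against 6.9. That is roughly 3–4% too long at the low end and 17–22% at the high end. Twelve-month EFS is overstated by about 2 to 10 percentage points. Censoring at the last assessment, including for later deaths, recovers the true median, but only because stopping was made independent of prognosis.

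**The case against.** The strongest reply is that EFS as defined depends only partly on assessment. Stopping for progression or a treatment-related adverse event, starting other anti-leukemia therapy, and death all count. SAP 7.5.3 accepts clinical progression determined by the investigator as relapse, and Appendix C of the AML response criteria accepts clinical or symptomatic progression as progressive disease. All of these can be learned at a contact without a marrow. This stands. It makes the bias smaller than for PFS and shrinks it further if follow-up captures such events, as the new-therapy columns show. It does not remove the bias, because the rule does not require any of this information at the censoring date.

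The follow-up and LFS provisions quoted come from the US MDS/CMML protocol. The SAP rests on Amendment 2.6 Europe, and its version history adds Amendment 2.7 Canada. Neither was supplied. Follow-up for conversion to AML does not fit subjects who already have AML. A reader might infer that AML subjects have telephone-only follow-up after treatment; the documents do not establish that.

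A reader might also take the lower rows of the first table as the expected size. They need 31% or 44% of subjects to stop assessment without an event, and nothing in the documents supports such proportions.

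Finally, a reader might treat the LFS rule as a full cure. LFS is a different endpoint in another population, and its rule leaves residual bias because deaths after unassessed gaps are still counted. Censoring at the last marrow or blood date also discards follow-up for death and new therapy. It may in effect censor transplanted subjects near transplant, although the SAP chose not to count transplant as an event.

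**Conclusion.** The point holds as a one-directional bias in a descriptive secondary endpoint. The SAP applies a survival censoring date to an endpoint containing progression and relapse, so subjects who leave assessment without a counted event but remain known alive inflate the EFS median and curve.

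The size cannot be derived from the documents. With the assumed 6-month median and only death detected later, 7% of subjects stopping early adds about 0.2 month (3%) and 18% adds about 0.5 to 0.6 month (8–10%). The effect is smaller if new therapy or clinical progression is captured. For subjects still on treatment the two censoring dates nearly coincide if AML subjects follow the supplied schedule, which has blood counts on Days 1 and 15 from Cycle 3.

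Confidence is high on the rule and the direction, and low on the size. The conclusion does not extend to the primary AUC analysis, its error rate or its power.

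**What to change.** In SAP 7.5.7, and in 7.5.8 for consistency:

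- Censor subjects without an event at the last adequate disease assessment showing no event. Define adequate as marrow, peripheral blood, or a documented investigator assessment of disease status.
- State how a death or other event after a long gap without assessment is handled, and define the gap. One option is to censor such subjects at the last assessment, in the main or a sensitivity analysis.
- Define post-baseline information in 7.5.7 as disease information, so that a survival contact alone does not satisfy it.
- Keep the last-known-alive rule as a sensitivity analysis, and report how many subjects have different censoring dates under the two rules.
- Check the follow-up schedule in Amendments 2.6 and 2.7 before settling the wording, and say how transplanted subjects are followed for this endpoint.

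The cost is SAP wording and a changed derivation. The estimate becomes slightly less favourable and some follow-up is discarded.
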